5.3.4 Assessment of Causality of Adverse Events

Investigators should use their knowledge of the patient, the circumstances surrounding the event, and an evaluation of any potential alternative causes to determine whether an adverse event is considered to be related to the study drug, indicating "yes" or "no" accordingly. The following guidance should be taken into consideration ([Table 3](#)):

- Temporal relationship of event onset to the initiation of study drug
- Course of the event, with special consideration of the effects of dose reduction, discontinuation of study drug, or reintroduction of study drug (as applicable)
- Known association of the event with the study drug or with similar treatments
- Known association of the event with the disease under study
- Presence of risk factors in the patient or use of concomitant medications known to increase the occurrence of the event
- Presence of non-treatment-related factors that are known to be associated with the occurrence of the event

Table 3 Causal Attribution Guidance

Is the adverse event suspected to be caused by the study drug on the basis of facts, evidence, science-based rationales, and clinical judgment?	
YES	There is a plausible temporal relationship between the onset of the adverse event and administration of the study drug, and the adverse event cannot be readily explained by the patient's clinical state, intercurrent illness, or concomitant therapies; and/or the adverse event follows a known pattern of response to the study drug; and/or the adverse event abates or resolves upon discontinuation of the study drug or dose reduction and, if applicable, reappears upon re-challenge.
NO	An adverse event will be considered related, unless it fulfills the criteria specified below. Evidence exists that the adverse event has an etiology other than the study drug (e.g., preexisting medical condition, underlying disease, intercurrent illness, or concomitant medication); and/or the adverse event has no plausible temporal relationship to administration of the study drug (e.g., cancer diagnosed 2 days after first dose of study drug).

5.3.5 Procedures for Recording Adverse Events

Investigators should use correct medical terminology/concepts when recording adverse events on the Adverse Event eCRF. Avoid colloquialisms and abbreviations.

Only one adverse event term should be recorded in the event field on the Adverse Event eCRF.

5.3.5.1 Injection Reactions

Injection reactions adverse events that occur during or within 24 hours after study drug administration should be captured as individual signs and symptoms on the Adverse Event eCRF rather than an overall diagnosis (e.g., record dyspnea and hypotension as separate events rather than a diagnosis of IT bolus-related reaction or anaphylactic reaction [see Section 4.5.5]).

5.3.5.2 Diagnosis versus Signs and Symptoms

For adverse events other than injection reactions (see Section 5.3.4) a diagnosis (if known) should be recorded on the Adverse Event eCRF rather than individual signs and symptoms (e.g., record only liver failure or hepatitis rather than jaundice, asterixis, and elevated transaminases). However, if a constellation of signs and/or symptoms cannot be medically characterized as a single diagnosis or syndrome at the time of reporting, each individual event should be recorded on the Adverse Event eCRF. If a diagnosis is subsequently established, all previously reported adverse events based on signs and symptoms should be nullified and replaced by one adverse event report based on the single diagnosis, with a starting date that corresponds to the starting date of the first symptom of the eventual diagnosis.

5.3.5.3 Adverse Events That Are Secondary to Other Events

In general, adverse events that are secondary to other events (e.g., cascade events or clinical sequelae) should be identified by their primary cause, with the exception of severe or serious secondary events. A medically significant secondary adverse event that is separated in time from the initiating event should be recorded as an independent event on the Adverse Event eCRF. For example:

- If vomiting results in mild dehydration with no additional treatment in a healthy adult, only vomiting should be reported on the eCRF.
- If vomiting results in severe dehydration, both events should be reported separately on the eCRF.
- If a severe gastrointestinal hemorrhage leads to renal failure, both events should be reported separately on the eCRF.
- If dizziness leads to a fall and consequent fracture, all 3 events should be reported separately on the eCRF.
- If neutropenia is accompanied by an infection, both events should be reported separately on the eCRF.

All adverse events should be recorded separately on the Adverse Event eCRF if it is unclear as to whether the events are associated.

5.3.5.4 Persistent or Recurrent Adverse Events

A persistent adverse event is one that extends continuously, without resolution, between patient evaluation timepoints. Such events should only be recorded once on the Adverse Event eCRF. The initial severity (intensity or grade) of the event will be recorded at the time the event is first reported. If a persistent adverse event becomes more severe, the most extreme severity should also be recorded on the Adverse Event eCRF. If the event becomes serious, it should be reported to the Sponsor immediately (i.e., no more than 24 hours after learning that the event became serious; see Section 5.4.2 for reporting instructions). The Adverse Event eCRF should be updated by changing the event from "non-serious" to "serious," providing the date that the event became serious, and completing all data fields related to serious adverse events.

A recurrent adverse event is one that resolves between patient evaluation timepoints and subsequently recurs. Each recurrence of an adverse event should be recorded as a separate event on the Adverse Event eCRF.

5.3.5.5 Abnormal Laboratory Values

Not every laboratory abnormality qualifies as an adverse event. A laboratory test result must be reported as an adverse event if it meets any of the following criteria:

- Is accompanied by clinical symptoms.
- Results in a change in study treatment (e.g., dosage modification, treatment interruption, or treatment discontinuation).

- Results in a medical intervention (e.g., potassium supplementation for hypokalemia) or a change in concomitant therapy.
- Is clinically significant in the Investigator's judgment.

It is the Investigator's responsibility to review all laboratory findings. Medical and scientific judgment should be exercised in deciding whether an isolated laboratory abnormality should be classified as an adverse event.

If a clinically significant laboratory abnormality is a sign of a disease or syndrome (e.g., alkaline phosphatase and bilirubin 5× upper limit of normal [ULN] associated with cholestasis), only the diagnosis (i.e., cholestasis) should be recorded on the Adverse Event eCRF.

If a clinically significant laboratory abnormality is not a sign of a disease or syndrome, the abnormality itself should be recorded on the Adverse Event eCRF, along with a descriptor indicating whether the test result is above or below the normal range (e.g., "elevated potassium," as opposed to "abnormal potassium"). If the laboratory abnormality can be characterized by a precise clinical term per standard definitions, the clinical term should be recorded as the adverse event. For example, an elevated serum potassium level of 7.0 mEq/L should be recorded as "hyperkalemia."

Observations of the same clinically significant laboratory abnormality from visit to visit should only be recorded once on the Adverse Event eCRF (see Section [5.3.5.4](#) for details on recording persistent adverse events).

5.3.5.6 Abnormal Vital Sign Values

Not every vital sign abnormality qualifies as an adverse event. A vital sign result must be reported as an adverse event if it meets any of the following criteria:

- Is accompanied by clinical symptoms
- Results in a change in study treatment (e.g., dosage modification, treatment interruption, or treatment discontinuation)
- Results in a medical intervention or a change in concomitant therapy
- Is clinically significant in the Investigator's judgment

It is the Investigator's responsibility to review all vital sign findings. Medical and scientific judgment should be exercised in deciding whether an isolated vital sign abnormality should be classified as an adverse event.

If a clinically significant vital sign abnormality is a sign of a disease or syndrome (e.g., high blood pressure), only the diagnosis (i.e., hypertension) should be recorded on the Adverse Event eCRF.

Observations of the same clinically significant vital sign abnormality from visit to visit should only be recorded once on the Adverse Event eCRF (see Section 5.3.5.4 for details on recording persistent adverse events).

5.3.5.7 Abnormal Liver Function Tests

The finding of an elevated ALT or AST ($>3 \times \text{ULN}$) in combination with either an elevated total bilirubin ($>2 \times \text{ULN}$) or clinical jaundice in the absence of cholestasis or other causes of hyperbilirubinemia is considered to be an indicator of severe liver injury (as defined by Hy's Law). Therefore, Investigators must report as an adverse event the occurrence of either of the following:

- Treatment-emergent ALT or AST $>3 \times \text{ULN}$ in combination with total bilirubin $>2 \times \text{ULN}$
- Treatment-emergent ALT or AST $>3 \times \text{ULN}$ in combination with clinical jaundice

The most appropriate diagnosis or (if a diagnosis cannot be established) the abnormal laboratory values should be recorded on the Adverse Event eCRF (see Section 5.3.5.5) and reported to the Sponsor immediately (i.e., no more than 24 hours after learning of the event), either as a serious adverse event or an adverse event of special interest (see Section 5.4.2).

5.3.5.8 Deaths

All deaths that occur during the protocol-specified adverse event reporting period (see Section 5.3.1), regardless of relationship to study drug, must be recorded on the Adverse Event eCRF and immediately reported to the Sponsor (see Section 5.4.2). This includes death attributed to progression of HD.

Death should be considered an outcome and not a distinct event. The event or condition that caused or contributed to the fatal outcome should be recorded as the single medical concept on the Adverse Event eCRF. Generally, only one such event should be reported. If the cause of death is unknown and cannot be ascertained at the time of reporting, "**unexplained death**" should be recorded on the Adverse Event eCRF. If the cause of death later becomes available (e.g., after autopsy), "unexplained death" should be replaced by the established cause of death. The term "**sudden death**" should not be used unless combined with the presumed cause of death (e.g., "sudden cardiac death").

If the death is attributed to progression of HD, "Huntington's Disease progression" should be recorded on the Adverse Event eCRF.

Deaths that occur after the adverse event reporting period should be reported as described in Section 5.6.

5.3.5.9 Preexisting Medical Conditions

A preexisting medical condition is one that is present at the screening visit for this study. Such conditions should be recorded on the General Medical History and Baseline Conditions eCRF.

A preexisting medical condition should be recorded as an adverse event only if the frequency, severity, or character of the condition worsens during the study. When recording such events on the Adverse Event eCRF, it is important to convey the concept that the preexisting condition has changed by including applicable descriptors (e.g., "more frequent headaches").

5.3.5.10 Lack of Efficacy or Worsening of HD

Events that are clearly consistent with the expected pattern of progression of the underlying disease should not be recorded as adverse events. These data will be captured as efficacy assessment data only. If there is any uncertainty as to whether an event is due to disease progression, it should be reported as an adverse event.

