4.5.3 Physical Examinations

A complete physical examination, performed at screening and other specified visits (see [Appendix 1](#)), should include an evaluation of the head, eyes, ears, nose, and throat, and the cardiovascular, dermatologic, musculoskeletal, respiratory, gastrointestinal, and neurological systems (including fundoscopy); genitourinary examinations may be performed as clinically indicated. The physical examinations should be conducted in the same manner on each occasion to ensure comparability to previous examinations. Height will be measured at screening only.

A neurologic examination should be performed at screening and other specified visits (see [Appendix 1](#)), and includes assessment of mental status, level of consciousness, cranial nerve function, motor function, sensory function, reflexes, and coordination. The neurologic examination should be conducted in the same manner on each occasion to ensure comparability to previous examinations. Neurologic examinations should be performed before and after treatment on each dosing day. Weight should also be measured at each neurologic examination.

Any abnormality identified at baseline should be recorded on the General Medical History and Baseline Conditions eCRF.

Changes from baseline abnormalities should be recorded in patient notes. New or worsened clinically significant abnormalities should be recorded as adverse events on the Adverse Event eCRF.

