4.5.8 Performance Outcome and Clinician-Reported Outcomes

Performance outcome (PerfO) and clinician-reported outcome (ClinRO) data will be collected via assessments to document the treatment effect of RO7234292. The assessments, translated into the local language as appropriate, will be completed in their entirety at specified timepoints during the study. To ensure instrument validity and that data standards meet health authority requirements, assessments will be self-administered or interviewer-administered (as appropriate) before the patient or clinician receives any information on disease status, prior to the performance of non-PerfO/ClinRO assessments, and prior to the administration of study treatment, unless otherwise specified.

Patients and clinicians may use paper forms or electronic devices to capture PerfO and ClinRO data. The paper forms, electronic devices, and/or instructions for completing the assessments will be provided by site staff. The data will be entered into the eCRF. The data will be available for access by appropriate study personnel.

The intent of the clinical measures (Huntington's disease-Daily Activities Scale [HD-DAS], TFC, Total Motor Scale [TMS], Independence Scale, Clinical Global Impression – Severity [CGI-S], Clinical Global Impression – Change [CGI-C], Montreal Cognitive Assessment [MoCA], Symbol Digit Modalities Test [SDMT], Stroop Word Reading Test [SWRT], and C-SSRS) is to assess the relationship of baseline clinical variables to biomarkers, i.e., to explore the cross-sectional relationship of clinical severity to

biomarker abnormalities, and secondly, to collect baseline clinical data prior to study drug administration and prior to enrollment in the OLE study for longer treatment, such that the clinical status and change in clinical status can be known in these individuals over time; no efficacy analyses are planned to be performed on clinical measure data collected for this study.

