Although functional HTT (mutant or wild-type) is essential for embryogenesis, near complete genetic ablation of HTT has little or no reported neurological effect in normal adult animals. However, complete ablation of wtHTT protein expression throughout life results in a worsening motor phenotype and, in male transgenic mice, age-dependent emergence of brain atrophy and decreased testicular size (Van Raamsdonk et al. 2005). In contrast, decreases in mHTT expression ameliorate disease and increases in mHTT exacerbate disease in animal models of HD, regardless of concomitant changes in wtHTT levels.

No clinically significant new neurologic events were observed in the completed Phase I/IIa study.

As a precaution a full neurological examination will be conducted as indicated in [Appendix 1](#).

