Appendix 3 Clinician-Reported Outcomes

Assessment	Name	Items	Concepts	Approx. Duration	Timing
MoCA	Montreal Cognitive Assessment	11	Overall cognitive status	10 min	Screening and Follow-up visits
HD-DAS	Huntington's Disease Daily Activities Scale	25	Daily function	25 min	Screening and Follow-up visits
IS	Independence Scale	1	Functional disability/independence	3 min	Screening and Follow-up visits
TFC	Total Functional Capacity Scale	5	Overall function	10 min	Screening and Follow-up visits
TMS	Total Motor Score	31	Motor function	15 min	Screening and Follow-up visits
C-SSRS	Columbia-Suicide Severity Scale	5	Suicidal ideation and behavior	20 min full version; 5 min follow-up version	Full version at Screening and follow-up version at Follow-up visit
CGI-S	Clinical Global Impression—Severity	1	Overall severity of patient status	2 min	Screening and Follow-up visits
CGI-C	Clinical Global Impression—Change	1	Overall change in patient status	2 min	Follow-up visit

Approx.=approximately.

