4.8.1 Describing Parameters over Time

All clinical outcomes will only be collected at Screening and follow-up visits, hence, descriptive tables (Table 5) will be presented at these two visits (including change from baseline at follow-up visit), while association analysis (Table 6) involving these parameters will only be presented at baseline.

As presented in Table 5, for PD biomarkers, descriptive tables will be presented per each time point and dose level. Additionally, for biomarkers, spaghetti plots (with overlaid median) for absolute, change and percent change from baseline values using untransformed data will be presented for all parameters by treatment dose level. In addition, individual patient profiles for selected biomarkers on absolute, change and percent change from baseline will be presented on the same page.

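### Worsening attributed to HD progression is kept off the AE form on the ground that efficacy assessments will record it, but no HD motor, functional or cognitive scale is scheduled between screening and follow-up or early termination

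*Protocol*

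**What the plan says.** Protocol 5.3.5.10 sets three rules:

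- Exclusion: "Events that are clearly consistent with the expected pattern of progression of the underlying disease should not be recorded as adverse events".
- Where excluded events go: "These data will be captured as efficacy assessment data only".
- Default: "If there is any uncertainty as to whether an event is due to disease progression, it should be reported as an adverse event".

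On the assessments that the second rule relies on:

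- Protocol Appendix 3 gives the timing of the MoCA, HD-DAS, Independence Scale, TFC, TMS and CGI-S as "Screening and Follow-up visits", and the CGI-C at follow-up only. Appendix 4 gives screening and follow-up for the SDMT and SWRT. Appendix 1 adds an early termination visit.
- SAP 4.8.1 agrees: "All clinical outcomes will only be collected at Screening and follow-up visits".
- Protocol 4.5.8 says that "no efficacy analyses are planned to be performed on clinical measure data collected for this study". SAP Table 5 tabulates most of these measures, with change from baseline, at follow-up.

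On examinations, Protocol 4.5.3 says "Changes from baseline abnormalities should be recorded in patient notes", and sends new or worsened clinically significant abnormalities to the AE form. Appendix 1 footnotes l and m and SAP 4.7.7 narrow that second route to findings outside expected variation or normal ageing. SAP 4.7.7 summarises examinations only through the case report form category in which they were recorded.

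**The concern.** The exclusion is justified by a second place where the event will be recorded. During treatment that second place is empty. An event judged to be clear progression is neither an AE nor a scale score, and an examination change seen the same way can end in the patient notes, which are not tabulated.

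This matters because some of the harms the protocol discusses can look like HD. Table 1 lists gait disturbance, altered cognition and altered continence as signs of suspected hydrocephalus. Section 5.1.2.1 reports an extension-study patient with hydrocephalus after chemical meningitis who also had speech and coordination difficulties. Section 5.1.2.8 notes that in animals "complete ablation of wtHTT protein expression throughout life results in a worsening motor phenotype".

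The study is open-label with no control arm, and every patient enters with unequivocal motor signs (diagnostic confidence level 4). Section 3.3.2 says such cohorts are known to decline. Progression is therefore a ready explanation, and there is no untreated group against which to test it. AE incidence and severity form a secondary endpoint (2.2.1), and AEs are among the data reviewed when deciding whether dose levels are repeated, lowered or added (3.1, 4.3.2).

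**Working it through.** The plan gives no figure to reproduce. The check sets the exclusion against the schedule and works out the interval.

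**Interval without an HD scale, for a patient who completes the study**

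Inputs: screening Day -28 to Day -3 and second dose on Day 29 (Appendix 1); follow-up 6 months ± 14 days after the last dose (Appendix 1); no Day 0 (SAP 2). Assumptions: 6 months = 183 days, and the second dose falls on its nominal day.

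- Follow-up: 29 + 183 = Day 212. Window: 212 − 14 = Day 198 to 212 + 14 = Day 226.
- Shortest gap, Day -3 to Day 198: 198 + 3 − 1 = 200 days.
- Longest gap, Day -28 to Day 226: 226 + 28 − 1 = 253 days.

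**What is scheduled from Day 1 to Day 127**

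| Assessment | Days | Count |
|---|---|---|
| HD motor, functional and cognitive scales | none | 0 |
| C-SSRS | 28, 43, 71, 127 | 4 |
| Neurological examination | 1, 4, 29, 43, 71, 127 (before and after dosing on Days 1 and 29) | 6 |

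Scale timing is taken from Appendices 3 and 4 and SAP 4.8.1, because the column position of some later marks in Appendix 1 could not be read with certainty. The other two rows are from Appendix 1.

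**Routes for a worsening seen during treatment**

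1. The investigator is uncertain whether it is progression: AE (5.3.5.10).
2. It is clinically significant and outside expected variation: AE (4.5.3, Appendix 1 footnotes l and m).
3. The investigator is confident that it is expected progression: barred from the AE form by 5.3.5.10, no HD scale due, and any examination change goes to patient notes. It reaches a scale only if it persists to follow-up or early termination.

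Route 3 is the gap.

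**Consistency with neighbouring rules**

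Section 5.3.5.9 records worsening of a pre-existing condition as an AE. Section 5.3.5.8 puts a death from HD progression on the AE form. Table 3 already allows underlying disease as a ground for judging an AE unrelated. The exclusion removes the event before that causality judgement is made.

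**The case against.** The strongest case against is that the exclusion is narrow and well fenced. It covers only events clearly consistent with progression, and any doubt makes the event an AE. AEs are sought at every contact (5.3.1). Six visits from Day 1 to Day 127 carry a neurological examination that can feed the AE form. Concomitant medication and changes in medical information are also recorded, and at dosing the latter includes physician visits for HD (Appendix 1 footnote ee). Table 1 treats new persistent or worsening gait disturbance as a sign of suspected hydrocephalus, to be worked up. The extension-study case was reported as a suspected unexpected serious adverse reaction, so it was not lost. The animal finding concerns complete, lifelong loss; the sentence before it reports little or no neurological effect of near-complete loss in normal adult animals, and this drug lowers the protein partially.

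All of that stands, and it rules out two stronger readings.

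- A reader might infer that HD-like harm on treatment is captured nowhere, or that no clinical scale is used. The documents do not support this: the default clause, the examinations and the C-SSRS all operate between screening and follow-up, and persistent worsening can appear in the follow-up scales.
- A reader might infer that a worsening beginning on Day 30 and gone by Day 127 would leave no record, shifting AE incidence by 1/4 = 25 percentage points in a dose group of 4. The protocol describes HD as progressive, so an episode that resolves would normally count as uncertain and be an AE. The 25 points is the weight of one patient; it does not measure what the rule, correctly applied, would remove.

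None of this supplies a record for the third route, where the investigator is confident.

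The body text also mentions interim testing: the MoCA at regular intervals (4.5.8.7) and the SDMT on a mobile app (4.5.8.8). Appendices 1, 3 and 4 schedule neither, and SAP 4.8.1, which takes precedence by the SAP's own statement in Section 2, excludes both. Even if done, they would add cognitive data only.

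**Conclusion.** The concern holds in a limited form. Section 5.3.5.10 relies on efficacy assessments that are not scheduled between screening and follow-up or early termination, a gap of about 200 to 253 days for a patient who completes the study. Worsening confidently attributed to HD progression in that gap has no AE or HD-scale record at the time. It does not enter the AE incidence endpoint or the AE data reviewed for later dose levels.

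The number of events affected cannot be estimated from the documents, and correct use of the uncertainty clause should keep it small. The point is worth fixing because, in an uncontrolled open-label study, the exclusion filters safety data by investigator judgement before causality is assessed, and the filter is easy to remove. The interval rests on 6 months = 183 days and a second dose on Day 29; the conclusion does not depend on either.

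**What to change.** 1. Protocol 5.3.5.10: remove the exclusion for this study. Any new or worsened clinically significant neurological, motor, cognitive or behavioural abnormality after the first dose is recorded as an AE, including when attributed to HD progression. Attribution is made at the causality step in 5.3.4. The clinical-significance threshold stays.
2. Appendix 1 footnotes l and m and SAP 4.7.7: delete the qualifier on expected variation so far as it would exclude HD progression. Otherwise it would reinstate the exclusion.
3. SAP 4.7.2: show AEs attributed to HD progression within all treatment-emergent AEs and again on a separate line.
4. Reconcile 4.5.8.7 and 4.5.8.8 with Appendices 1, 3 and 4: either schedule the interim MoCA and app-based SDMT or delete the references.

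The cost is protocol and SAP wording and a few more AE pages. Items 1 to 3 add no visits or procedures. Some expected progression will enter the AE tables, where the separate line identifies it. That line still rests on unblinded investigator attribution, but the events are then visible and can be reviewed.
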